To address the secondary objective, participants will also be asked to provide pre- and post-travel biologic (stool) samples for laboratory testing for the presence of gut AMR genes (see Laboratory instruments). Timing of the pre- and post-travel data and stool sample collections will be within 7 days before departure and 10 days after return from travel, respectively. Both biologic (stool) samples will be self-collected and submitted by mail to the clinic (the collection kit, and all necessary packaging and postage will be provided to the traveler). The participant will not be seen by a healthcare provider involved with the study post-travel unless they are ill and seek an evaluation.

As part of standard pre-travel consultation practices, if indicated, travelers will be prescribed anti-diarrheal medications and/or antibiotics for self-treatment of TD. These medications may include loperamide (Imodium), diphenoxylate and atropine (Lomotil), BSS (Pepto bismol), ciprofloxacin, azithromycin, or rifaximin. If these medications are taken while abroad, the travelers will be asked to note this on the during travel or post-travel questionnaires.

No difference in pre-travel advice, provision of anti-diarrheal medications, or during- or after-travel medical evaluation or advice will occur based on the traveler's assigned study arm.

Duration of Subject Involvement

The duration of each participant's involvement in the study is expected to be a maximum of 6 weeks. This will account for time to complete the pre-travel consultation/enrollment visit, 21 days (or less) of travel, and post-travel follow-up.

How the Study Design Addresses the Objectives and Hypotheses

A double-blinded, placebo-controlled randomized clinical trial is the best study design to address the study objectives and hypotheses. We aim to determine if there is a biologic benefit to an intervention (BSS administration), and a placebo-controlled methodology is required to determine if there is a statistically significant benefit of the intervention

regarding incidence of TD and acquisition of gut AMR genes. It is imperative to blind both healthcare providers and participants to ensure that biases, including selection and observer bias, are minimized.

Stakeholder Participation

The primary stakeholders for the project are international travelers, healthcare providers, and public health officials.

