Includes the 7 days prior to departure in which the pre-travel questionnaire and a biologic (stool) specimen is collected, the full duration of travel, and through 10 days maximum post-return from travel, or until both the post-travel questionnaire and submission of the post-travel biologic (stool) specimen is complete (a maximum of 17 days post-travel)

Travel companion (group):

Two or more study participants with a common relation (friends, colleagues, or relatives) with the same itinerary, who anticipate performing the same activities during travel

Trip duration:

The number of days spent in country; excludes air travel time

Severe TD:

Hospitalization to an inpatient ward either during travel or after travel with a diagnosis of diarrhea

Acquisition of AMR gene(s):

The presence in a post-travel biologic (stool) specimen of one or more antimicrobial resistance gene(s) that were not present in a pre-travel biologic (stool) specimen from the same person, and which is known to confer antimicrobial resistance to one or more antimicrobial agents ("resistome")

Medication compliance:

Full = participant takes all scheduled doses according to directions

Good = If <15% of BSS or placebo doses were missed during travel

Fair = If 15–30% of BSS or placebo doses were missed during travel

Poor = If >30% of doses were missed during travel

Questionnaire compliance:

Full = participant completes all questionnaires

Good = participant completes >80% of all during travel questionnaires, AND
both the pre- and post-travel questionnaires

Fair = participant completes between 30–80% of all during travel
questionnaires, including AT LEAST the pre-travel questionnaire

Poor = participant completes <40% of all during travel questionnaires, and AT
LEAST the pre-travel questionnaire

Biologic (stool) specimen compliance:

Full = BOTH specimens collected and sent

Fair = ONLY one specimen collected and sent

Poor = No specimens collected and sent

Loss to follow-up:

Failure to complete the post-travel questionnaire after three attempts to contact the participant or if submission of the post-travel biologic specimen (stool) occurs more than 10 days after return from travel or is not submitted

Participant Inclusion Criteria

Willing participants must meet the inclusion criteria as outlined here:

1. Be ≥ 18 and <70 years of age at the time of enrollment

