Once recruited and consented, eligible participants will be registered in the study at the clinic site and receive a one-page instructional handout regarding stool specimen collection and questionnaire completion [**APPENDIX K**]. All primary participant information will be kept at the clinic. Travelers will agree to inform the study personnel at their clinic site if they have a change in travel plans, begin a course of antibiotics, become pregnant before or during travel, or develop diarrhea before departure, to determine if they are still eligible to participate. In the event that a participant withdraws from the study at any time, the clinic must note this in the study database.

Description and Justification of Compensation

Gift card compensation will be provided to the participants for the time spent on this project.

The participant will receive \$100 for completion of the pre-travel questionnaire and the submission of a pre-travel biologic (stool) specimen. For each daily questionnaire that the participant completes while traveling, they will receive an additional \$5 (maximum additional \$100). The participant will receive an additional \$50 for completion of the web-based post-travel questionnaire and an additional \$50 for the submission of a biologic (stool) specimen post-travel. The maximum compensation will be \$300 total. The minimum participation to receive compensation is good medication compliance, good questionnaire compliance, and good biologic (stool) specimen compliance (see Definitions).

Compensation will be mailed to participants upon completion of their study period.

Statement of Extra Costs to Participants Due to their Involvement in the Study

We do not anticipate any extra costs to the participants due to their involvement.

Procedures for Implementing and Documenting Informed Consent

The New York Center for Travel and Tropical Medicine clinic must obtain and ensure scientific and ethical permission, in accordance with state and national regulations. All collaborators must adhere to strict guidelines to ensure participant confidentiality, following the Privacy Act. Biological specimens (stool) must be processed per established safety protocols.

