Dosing will begin on the flight prior to arrival in the destination and will cease once they return home. The study medications must be taken twice daily (a morning and an evening dose); with time zone changes, the first dose should be taken to ensure that no longer than 12 hours passes before a subsequent dose.

Before departure, participants will be provided, free of charge, all needed study medication for the duration of their trip. Participants will be encouraged to take all doses of their medication and appropriately document on their daily during travel questionnaires if a dose was missed or taken off schedule.

Outcomes

The outcomes of this study will include:

	Favorable Outcome	Non-favorable Outcome
Hypothesis 1: Prevention of TD	Prevention of TD in the intervention group	TD in the intervention group at a rate similar to placebo; intervention drug side effects; adverse events

Hypothesis 2: Acquisition of AMR genes	Reduced or no presence of travel-associated gut AMR genes in the intervention group	No reduction in the presence of travel-associated gut AMR genes in the intervention group
---	---	---

The participant's study period will end in the following circumstances:

1. The traveler meets criteria for removal (see Criteria for Removal from the Study)
2. The participant voluntarily withdraws from the study (see Procedures for Implementing and Documenting Informed Consent)
3. The participant completes all study activities and submits all study questionnaires and biologic (stool) specimens
4. The participant is lost to follow-up

The participants will be instructed at enrollment to stop the study medication for any of the following reasons (although they will still be instructed to answer their questionnaires and submit biologic [stool] specimens as scheduled):

1. Antibiotics or BSS (either provided by the study personnel for TD treatment, or taken as an over-the-counter remedy) are taken for TD or for another medical condition
2. Any severe adverse events as described, such as signs and symptoms of salicylism or neurotoxicity, occur
3. Hospitalization for any reason

Barring the reasons listed above, the study medication should be taken throughout the trip duration, even if diarrhea occurs, if possible.

Criteria for Removal from the Study

Participants will be removed from the study when any of the following criteria apply:

1. Do not complete the pre-travel questionnaire (see Definitions for compliance)
2. Loss to follow-up (see Definitions)

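### Payment requires fewer than 15% of doses missed, with no stated exemption for instructed stops, and the adverse-event stop rule is worded in two ways

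*Combined protocol and SAP*

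**What the plan says.** **Payment.** Description and Justification of Compensation gives the rationale as "Gift card compensation will be provided to the participants for the time spent on this project". It then lists payments for questionnaires and stool specimens, up to $300, and sets a floor: "The minimum participation to receive compensation is good medication compliance, good questionnaire compliance, and good biologic (stool) specimen compliance (see Definitions". Under Definitions, the relevant medication category reads "Good = If <15% of BSS or placebo doses were missed during travel". The category above it reads "Full = participant takes all scheduled doses according to directions". The During Travel part of Study Instruments takes missed doses from the tablet counts that participants report each day.

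**Instructed stops.** The Outcomes section says "The participants will be instructed at enrollment to stop the study medication for any of the following reasons", with the rider "although they will still be instructed to answer their questionnaires and submit biologic [stool] specimens as scheduled". The reasons are antibiotic or BSS use, a severe adverse event such as signs of salicylism or neurotoxicity, and any hospitalization. The first is worded "Antibiotics or BSS (either provided by the study personnel for TD treatment, or taken as an over-the-counter remedy) are taken for TD", and it also covers use for other conditions. Outside these reasons, tablets continue where possible, even through diarrhea. The Procedures section makes the first trigger foreseeable: when indicated, "travelers will be prescribed anti-diarrheal medications and/or antibiotics for self-treatment of TD", and BSS is among the drugs named.

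**Stated exemption.** Criteria for Removal from the Study preserves payment only for participants whom the co-principal investigators remove for safety or study integrity (reason 6).

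**Adverse events.** Identifying, Managing, and Reporting Adverse Events tells a traveler who has an adverse event abroad to stop tablets and call the study team. It sets no severity limit. The list that opens the section has two items: side effects (constipation, tinnitus, dizziness), and adverse events such as neurologic signs of salicylate toxicity.

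**The concern.** A participant who stops tablets as told stays in the study and does the same paid work as anyone else. If the doses that follow count as missed, that person falls below the payment floor for obeying an instruction, although payment is said to be for time. The reason-6 exemption does not help, because the person has not been removed.

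The incentive acts during travel. A participant who believes that payment is at stake has a reason to keep taking tablets after a stop trigger, or to overstate the daily tablet count. The first bears on safety. A traveler who treats diarrhea with BSS and continues blinded active tablets takes salicylate from two sources. The second bears on the adherence data, which are self-reported; the available text describes no count of returned tablets. Lenient handling by staff afterwards would undo neither.

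The two adverse-event instructions add to this. A traveler with tinnitus or constipation could be told to continue under one section and to stop under the other, without knowing whether stopping affects payment.

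**Working it through.** **1. The plan's own payment figures.** Maximum per participant: 100 (pre-travel questionnaire and stool) + 100 (daily forms at $5 each, capped) + 50 (post-travel questionnaire) + 50 (post-travel stool) = $300, as stated. Budget Table 4: 500 × 300 = $150,000, as stated. The budget therefore already covers full payment to all 500 participants.

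**2. Inputs.** Two doses a day (Intervention). Trips of 7 to 21 days in country (Inclusion Criteria). The good category requires fewer than 15% of doses missed (Definitions).

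**3. Missed-dose allowance.** Scheduled doses n = 2 × days. The allowance is the largest k with k/n < 0.15. Payment with every item completed = 100 + min(100, 5 × days) + 50 + 50.

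| Trip | n | Allowance k | k/n | (k+1)/n | Days covered, k/2 | Payment at stake |
|---|---|---|---|---|---|---|
| 7 days | 14 | 2 | 14.3% | 21.4% | 1 | 100 + 35 + 100 = $235 |
| 14 days | 28 | 4 | 14.3% | 17.9% | 2 | 100 + 70 + 100 = $270 |
| 21 days | 42 | 6 | 14.3% | 16.7% | 3 | 100 + 100 + 100 = $300 |

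If doses after a stop count as missed, and no other dose was missed, a permanent stop keeps payment only when it falls within about the last 1, 2 or 3 days.

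**4. A stop near mid-trip, same reading.** 7 days, after day 3: 8/14 = 57% missed. 14 days, after day 7: 14/28 = 50%. 21 days, after day 10: 22/42 = 52%. All exceed 30%, which Definitions calls poor.

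**5. Sensitivity to flight doses.** Dosing starts on the outbound flight and ends on return home. The number of flight doses is not given, so 2 or 4 extra is an assumption. With 2 extra, n = 16, 30, 44; with 4 extra, n = 18, 32, 46. The allowance stays at 2, 4 and 6. The closest case is 7/46 = 15.2%, which still fails.

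**6. The two stop rules side by side.**

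| | Outcomes | Adverse-event section |
|---|---|---|
| Trigger | Severe adverse events, with toxicity signs as the example | An adverse event, severity not limited |
| Mild side effects | Not on the stop list, so continue | Inside the section's opening list of adverse events, but labelled side effects |
| Action | Stop tablets, keep reporting | Stop tablets, contact the study team |

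The two agree if adverse event in the second section means only its second list item. They conflict if the opening list defines the term.

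**The case against.** The strongest reply is that a forbidden dose is not a missed dose. The During Travel section says tablets are taken throughout travel unless a study outcome or a removal criterion is reached, and it points to the Outcomes section, where the stop list sits. The full-compliance definition counts scheduled doses taken as directed. On that reading the schedule ends at the stop, and nobody loses payment for obeying it. The payment floor also cannot be applied word for word: it asks for good stool-specimen compliance, but Definitions gives only full, fair and poor. And the consent form, which covers compensation, is not in the review copy and may settle the matter.

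Much of this stands. The lenient reading is a fair one, and the text does not choose between the two. But the words about directions belong to the full category, whereas payment turns on the good category, which speaks only of doses missed. Missed doses are derived from tablet counts, and the one written exemption covers a different group.

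A reader might also infer that many participants would lose payment. The documents do not support a headcount. They give no rate of antibiotic or BSS use during travel, and Description of Risks to the Participant says antibiotics are advised only for severe diarrhea, which points to the low end. BSS self-treatment remains possible.

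On adverse events, the separate labels for side effects and adverse events allow the sections to agree, and the outcomes table keeps the same distinction. Calling the study team would resolve some doubtful cases. The section's opening nevertheless gathers both items under adverse events, so the narrower reading is available but not settled.

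**Conclusion.** The point holds as a defect of wording. Read literally, the payment floor lets a participant forfeit $235, $270 or $300 by obeying a stop more than about 1, 2 or 3 days before the end of a 7-, 14- or 21-day trip. This assumes that doses after the stop count as missed, that no other dose was missed, and that every paid item was completed.

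It would go too far to say that the plan withholds payment from those who follow a safety instruction. The text leaves that open, and the consent form could not be checked. It would also go too far to call the two stop rules a flat contradiction: they conflict on the broad reading of adverse event and agree on the narrow one.

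Both ambiguities act on participants while they are abroad and bear on safety, and both are cheap to remove, so they should be fixed. The number affected cannot be estimated from the documents. Sample size and primary analysis are unaffected.

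**What to change.** 1. In Definitions and in the compensation section, and in the consent form if it is silent, state that doses after a protocol-instructed stop are not counted as missed for compensation. Verify the stop from items already on the daily form: medications started, inpatient admission, symptoms and comments.
2. In the adverse-event section, replace the unqualified trigger with the Outcomes threshold: stop for severe events or for signs of salicylate toxicity or neurotoxicity. For milder side effects, contact the study team, and exempt any dose held on their advice.

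The cost is a few sentences and a short IRB amendment. No budget is added, since full payment for 500 participants is already funded. The adherence incentive stays for everyone not told to stop. The downside is a small risk of false stop claims, which can be checked against the daily form.

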2. Sign an informed consent (see Procedures for Implementing and Documenting Informed Consent) stating willingness to participate and comply with the study protocol
3. Plan on leaving for an international trip ≥ 7 days after their pre-travel consultation
4. Plan on traveling in country for ≥ 7 days but ≤ 21 days (21 day limit due to BSS duration recommendations and a lack of data on longer-term BSS use) (see Definitions)
5. Traveling to either South East Asia, South Central Asia, North Africa, or Sub-Saharan Africa for at least 7 days of their itinerary (see **APPENDIX B** for list of countries classified to each region)
6. Be willing to complete an initial eligibility screening (see Recruitment and Enrollment)
7. Be willing to complete questionnaires and provide biologic specimens (stool) within 7 days of departure and within 10 days after return
8. Be willing to refrain from taking any pre-biotics, probiotics, synbiotics and/or herbal supplements throughout their study period

Participant Exclusion Criteria

Willing participants must not meet any exclusion criteria as outlined here:

1. Are <18 years of age or >69 years of age
2. Are traveling in country for <7 or >21 days (see Definitions)
3. Have known or suspected contraindications to taking BSS (including, but not limited to, travelers with kidney disease, diabetes, gout, a clotting disorder, or an allergy to any component of BSS)

4. Are pregnant (via self-report), are planning to become pregnant, or may become pregnant during travel (not actively using contraception and are sexually active), or are breastfeeding
5. Routinely take a medication known to interact with BSS (including, but not limited to, insulin, methotrexate, valproic acid, ACE inhibitors, anticoagulants, or other salicylates) (see **APPENDIX A** for complete list)
6. Have taken an antibiotic in the 30 days before departure
7. Have taken any medications that may lower one's ability to fight infection (e.g., steroids, monoclonal antibodies, etc.)
8. Have previous diagnoses of immunocompromising conditions such as HIV/AIDS, complement deficiency, immunoglobulin deficiency, or undergoing active chemotherapy or participants with chronic gastrointestinal disorders, such as chronic diarrhea, irritable bowel syndrome (IBS), inflammatory bowel disease (i.e., Crohn's disease, ulcerative colitis), celiac disease, malabsorption syndromes, pancreatic insufficiency, gallbladder disease, or current gastrointestinal cancer

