Participants will be asked to submit a web-based post-travel questionnaire within 10 days after return from travel, submit a biologic (stool) specimen, and provide all daily questionnaires that were completed during travel. This will be submitted via a pre-paid envelope addressed to the study clinic that was given to the participant when enrolled.

Study personnel will make follow-up telephone calls on days 3, 5, 7, and 10 after return as needed to encourage that the post-travel questionnaire, paper questionnaires from during-travel, and biologic (stool) specimens are all submitted.

The web-based post-travel questionnaire will include questions on:

1. The development of symptoms of TD since returning from abroad, including duration of symptoms
2. New antibiotic or other medication use
3. Adverse events

4. Contact with healthcare facilities or providers
5. Changes to travel itinerary during travel

Table 2. Schedule of CLINIC events (primary and secondary objectives):

	Stages			
	Pre-travel consultation (baseline)	Pre-travel (≤ 7 days before departure)	During travel	Post-travel (≤ 10 days after return)
Screening Questionnaire	X			
Informed Consent	X			
Pre-travel Questionnaire*		X		
Follow-up call(s)		X		X [†]
During travel Questionnaires			X	
Post-travel Questionnaire				X
Adverse Events Reporting			X	X

*Study personnel will call the participant to complete a pre-travel questionnaire 7 days before departure and to ensure that answers to the questions on the screening questionnaire have not changed. Reminder calls will occur as per **APPENDIX G**. If the traveler is leaving exactly 7 days after the pre-travel consultation/enrollment visit, this questionnaire can be performed at the pre-travel consultation/enrollment visit.

[†]Study personnel will call the participant within 3 days of return from travel to remind participants to complete their web-based post-travel questionnaire, submit any paper during travel questionnaires, and collect and submit the post-travel biologic (stool) sample. Reminder calls will occur as per **APPENDIX G**.

Laboratory Instruments

All participants will collect and submit a fresh biologic (stool) sample in the 7 days before departure and within 10 days after return. Participants will be

provided all instructions and materials necessary to collect and submit these samples at enrollment. All biologic (stool) specimens will be submitted by mail, and participants will be given pre-paid shipping materials.

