Participants will be provided two OMNIgene gut kits at their pre-travel consultation/enrollment visit once enrolled (see Biologic [Stool] Specimen Data Collection and Testing). These kits will come with instructions on use, handling, and shipment.

In the event that participants are able to provide a stool sample while in clinic for their pre-travel consultation/enrollment visit or during a non-study post-travel follow-up sick visit within 10 days of return, these samples will be aliquoted by study personnel at The New York Center for Travel and Tropical Medicine in the following manner:

*First, the required quantity will be placed in the participant's OMNIgene gut kit (per manufacturer directions) to be sent to CDC's Clinical and Environmental Microbiology Branch for resistome testing. The remainder will be frozen, and sent to CDC for analysis at a later date (note: OMNIgene gut kit does not allow for culture - a see Biologic [Stool] Specimen Collection and Testing). Only those participants who happen to have a biologic (stool) specimen collection completed at the clinic will have their stool analyzed by culture; this is not a requirement for participation and no additional compensation above that previously described will be offered.

Table 3. Schedule of LABORATORY events (secondary objective)

(Events from Table 2 still apply to these participants)

	Stages		
	Pre-travel	During travel	Post-travel
Biologic (stool) sample	X		X
Laboratory testing of stool	X		X

Analytic tests

Questionnaires: Data from the questionnaires will be analyzed for statistical significance comparing intervention vs placebo groups.

Biologic (stool) specimens: A highly multiplexed PCR assay detecting over 500 different AMR genes will be used to test the DNA extracted from all biologic (stool) specimens that were placed in the OMNIgene gut kit (see Biologic (Stool) Specimen Collection and Testing). Results will be analyzed to determine if the participants acquire gut AMR genes (changes to the “resistome”) as a result of travel and whether or not that change varied with the bismuth subsalicylate treatment received. Additionally, stool bacteriologic culture will be performed on those specimens submitted in clinic.

Intervention

We propose the inclusion of two arms to test BSS against placebo:

1. BSS 4 tablets po bid (2.1 grams total)
2. Placebo 4 tablets po bid

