APPENDIX A: Screening Questionnaire

Screening Questionnaire

Script [read to all travelers]: Hello, my name is [name] and I am a [role in the clinic] at The New York Center for Travel and Tropical Medicine. We are conducting a study of international travelers to see if bismuth subsalicylate (or BSS) can help to prevent travelers' diarrhea. Participation in this questionnaire to see if you are eligible is voluntary, and it will only take a moment of your time. We will be collecting your email address, so in the event that you are eligible to participate, we can send you the study questionnaires and reminder emails; your email will only be used for study purposes. Are you interested in seeing if you are eligible to participate?

YES NO

[If "yes", please complete the following with the traveler]:

Participant's Initials		Date	
Age			

Participant Email (REQUIRED): _____
 Participant Phone #1 (OPTIONAL): _____ Participant Phone #2 (OPTIONAL): _____

1. Are you ≥ 18 years of age and <70 years of age?

Yes* No Don't know

2. Are you traveling to either South East Asia, South Central Asia, North Africa, or Sub-Saharan Africa?

Yes* No Don't know

3. Are you spending at least 7 days and no more than 21 days in these regions?

Yes* No Don't know

4. Are you leaving for your trip in at least 7 days?

Yes* No Don't know

5. Are you now pregnant or nursing or do you plan to get pregnant before the end of your trip?

Yes No* Don't know

6. Do you have known or suspected allergy to bismuth, salicylate, or aspirin?

Yes

No*

Don't know

7. Do you have known or suspected allergy to microcrystal cellulose, calcium carbonate, artificial coloring, magnesium, mannitol, povidone, saccharin, or talc?

Yes

No*

Don't know

8. Do you have kidney disease, diabetes, gout, or a clotting disorder?

Yes

No*

Don't know

9. Have you taken an antibiotic in the past 30 days? For example:

- Doxycycline or minocycline
- Flagyl, cotrimoxazole (e.g., Bactrim, Septra)
- Penicillins (e.g., amoxicillin, Augmentin)
- Cephalosporins (e.g., Keflex)
- Fluoroquinolones (e.g., ciprofloxacin)
- Macrolides (e.g., azithromycin [Zithromax], erythromycin)

Yes

No*

Don't know

10. Do you take any of the following medications or therapies?

- Chronic oral or intravenous IV steroids (e.g., hydrocortisone or prednisone); not inhaled steroids
- Alkylating agents (e.g., cyclophosphamide [Cytoxan])
- Antimetabolites (e.g., azathioprine [Imuran], 6-mercaptopurine [Purinethol])

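### Stool given at the pre-travel consultation may serve as the resistome baseline with no day limit, although the protocol's own rules put that visit in the 7-day window only when departure is exactly 7 days later

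*Combined protocol and SAP*

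**What the plan says.** Four places set the baseline window. Procedures states that "stool sample collections will be within 7 days before departure and 10 days after return from travel, respectively". Laboratory Instruments repeats it: "All participants will collect and submit a fresh biologic (stool) sample in the 7 days before departure". The Study period definition and inclusion criterion 7 agree.

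Two places fix the visit relative to departure. Inclusion criterion 3 reads "Plan on leaving for an international trip ≥ 7 days after their pre-travel consultation", and question 4 of the screener (Appendix A) asks "Are you leaving for your trip in at least 7 days", which must be answered yes.

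Laboratory Instruments then adds the clinic route: "In the event that participants are able to provide a stool sample while in clinic for their pre-travel consultation/enrollment visit", study staff first fill the participant's kit, "to be sent to CDC's Clinical and Environmental Microbiology Branch for resistome testing", and freeze the remainder. The section on stool specimen collection and testing repeats this route and says that each participant receives two kits, one pre-travel and one post-travel. In both places the post-travel sick visit carries its 10-day limit and the pre-travel visit carries none.

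The Table 2 footnote deals with the coincidence of visit and window for the questionnaire only: "If the traveler is leaving exactly 7 days after the pre-travel consultation/enrollment visit", the questionnaire may be done at the visit.

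**The concern.** Followed literally, the clinic route produces baselines outside the protocol's own window. A sample taken at the visit uses the only pre-travel kit, so an in-window sample would not normally follow. The definition of AMR gene acquisition compares the post-travel specimen with a pre-travel specimen and puts no timing condition on the latter. A post-travel sample later than 10 days counts as loss to follow-up, but a baseline that is too early has no consequence.

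At stake is the secondary objective. The analysis is meant to identify genes gained as a result of travel. Time at home between the visit and departure is not travel, and changes in the resistome over that time would enter the endpoint.

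**Working it through.** **Sample size.** The only computed design figure is 488. Two-sided alpha 0.05, 80% power, 0.40 vs 0.28 and pooled variance without continuity correction give 244 per arm, 488 in total, as stated. The point does not touch it.

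**Timing.** Let departure be day 0. Inclusion criterion 3 puts the visit on day -7 or earlier. The window runs from day -7 to day 0. The intersection is day -7 alone.

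**Share out of window.** The documents give no lead times. Assume lead time is uniform over whole days from 7 to L. The in-window share is 1/(L - 6).

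| L (days) | In window | Out of window |
|---|---|---|
| 10 | 25.0% | 75.0% |
| 14 | 12.5% | 87.5% |
| 28 | 4.5% | 95.5% |
| 56 | 2.0% | 98.0% |

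**Direction.** Take one gene. Assume that 30% of those without it at departure acquire it, and 60% of those with it at departure still have it after travel.

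- Stable carriage: prevalence 10%, mean carriage 20 to 60 days. With P the chance of gaining the gene between visit and departure, apparent acquisition is 0.90 × [(1 - P) × 0.30 + P × 0.60]. A baseline at departure gives 0.90 × 0.30 = 27.0%. A baseline 7 days too early with 60-day carriage (P = 0.012) gives 27.3%. A baseline 35 days too early with 20-day carriage (P = 0.086) gives 29.3%. The error is upward.
- Declining carriage, for example after a recent trip: prevalence 40% at the visit, mean carriage 20 days, no background gain. The early baseline gives 0.60 × 0.30 = 18.0%. A baseline at departure gives (1 - 0.40 × exp(-7/20)) × 0.30 = 21.5% when the gap is 7 days and (1 - 0.40 × exp(-35/20)) × 0.30 = 27.9% when it is 35 days. The error is downward.

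**Effect on the contrast (illustrative).** Assume acquisition of 50% on placebo and 36% on BSS, a true difference of 14 points. Let e be the same error rate in both arms. Assume 5% to 20% of participants give a clinic baseline and 10% to 30% of those are misclassified, so e runs from 0.05 × 0.10 = 0.005 to 0.20 × 0.30 = 0.06.

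- False gain: each proportion p becomes p + e(1 - p), so the difference becomes 14 × (1 - e). At e = 0.06 this is 53.0% vs 39.8%, or 13.2 points.
- Masking: p becomes p(1 - e), and the difference is again 14 × (1 - e). At e = 0.06 this is 47.0% vs 33.8%, or 13.2 points. The ratio stays at 0.72, whereas under false gain it moves to 0.398/0.530 = 0.75.

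Power, two-sided alpha 0.05:

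| n per arm | No error | False gain, e = 0.005 | False gain, e = 0.06 | Masking, e = 0.06 |
|---|---|---|---|---|
| 244 | 88.0% | 87.6% | 83.2% | 84.4% |
| 125 | 61.0% | 60.5% | 55.1% | 56.4% |

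The first row borrows the n set for travelers' diarrhea. The second splits equally the 250 participants for whom Table 5 budgets diagnostic stool testing. Neither is a planned power for AMR acquisition, because the documents give none.

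**The case against.** The strongest defence is that the text already requires an in-window sample from everyone and that the day -7 call reminds participants to send it, so the clinic sample might be read as an extra. That reading fails on the kits: the clinic specimen goes into the participant's own kit for resistome testing, and only one kit is allotted to the pre-travel sample.

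A second defence is that other rules limit drift during the gap. Antibiotics in the 30 days before departure are an exclusion, as is diarrhea before departure. Probiotics and herbal supplements are to be avoided, and eligibility is rechecked by telephone. This stands as a reason to expect a small error, but it does not bring the sample into the window.

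A reader might infer three stronger things that the documents do not support:

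- **That early baselines inflate acquisition.** The introduction describes carriage as transient in most travelers, travel in the past 90 days is recorded but not excluded, and antibiotic use 30 to 90 days before travel is tabulated. Genes lost before departure would hide later acquisition, so the sign is open.
- **That one arm gains.** Dosing starts on the flight and allocation is randomized and blinded, so the timing error should not differ by arm.
- **That clinic samples almost always miss the window.** This is plausible, but it depends on lead times that are not given.

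**Conclusion.** The inconsistency is real, and nothing elsewhere in the protocol resolves it. A clinic-visit baseline meets the protocol's window only when planned departure is exactly 7 days after the visit. The result can be misclassified acquisition in either direction, expected to be equal by arm, which tends to dilute the BSS contrast on the secondary AMR objective.

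The size is unknown. It depends on the share of participants using an optional route, on their lead times and on background gene turnover, none of which is stated. Under the assumed rates above, a 14-point difference shrinks by less than 1 point. The power figures are illustrative only, since they rest on assumed acquisition rates and a chosen n per arm. This is a minor point, worth correcting because the correction is cheap.

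**What to change.** In Laboratory Instruments and in the section on stool specimen collection and testing, carry over the Table 2 footnote rule: an in-clinic pre-travel specimen is the resistome baseline only when departure is exactly 7 days after the visit. Otherwise keep that specimen for culture and freezing, and reserve the pre-travel kit for the home sample in the 7 days before departure.

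Record the collection date of every specimen. Prespecify a sensitivity analysis of AMR acquisition that excludes any baseline outside the window.

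The cost is a sentence in each of the two sections, a date field and one extra analysis. A few participants would give a second sample, using a kit they already hold, and some may not return it, which would leave them without a usable baseline.
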